9.3 Definition of Populations

Adults aged 18 years and above, with mild to severe persistent asthma will be enrolled. Subjects will have asthma which is not optimally controlled despite the current use of inhaled corticosteroids with or without inhaled long-acting beta agonists. The populations will be those subjects randomized to the placebo arm versus ginger extract arm.

All randomized subjects will be included in the primary analysis, analyzed based on intention-to-treat. In addition, a secondary analysis based on per protocol will be conducted. Per protocol analysis will exclude patients who missed 30% or more of their assigned treatment. Please refer to section 5.4 for the equation to calculate compliance.

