Day 43-50/Visit 4: Subjects will be asked to withhold morning dose of the study drug the day of the study visit. Women of child bearing potential will have a negative urine pregnancy test confirmed. Subjects will be asked to complete an ACT to assess asthma control and a validated asthma quality of life questionnaire (Juniper mini AQLQ). FeNO will be measured using a Circassia Niox Vero machine with disposable filters. Basic spirometry will be performed, Methacholine test will be performed if subject meets safety criteria ($FEV_1 > 1.5L$ or 60% predicted). 10ml of blood will be collected for measurement of cytokines, biomarkers and blood eosinophil count. For those patients in PK group, an additional 35 ml of blood will be collected over an additional 7 times points (pre-dose, 0.5 hour, 1 hour, 2 hour, 3 hour, 4 hour, and 8 hour). Study drug will be administered in the clinic after the pre-dose PK blood draw.

Unused study medication will be collected and pill count will be recorded.

Day 71-78/Visit 5: Subjects will be asked to withhold morning dose of the study drug the day of the study visit. Women of child bearing potential will have a negative pregnancy test confirmed. Subjects will be asked to complete an ACT to assess asthma control and a validated asthma quality of life questionnaire (Juniper mini AQLQ). FeNO will be measured using a Circassia Niox Vero machine with disposable filters. Basic spirometry will be performed. Methacholine hyperresponsiveness will be measured if subject meets safety criteria ($FEV_1 > 1.5L$ or $>60\%$ predicted). 10ml of blood will be collected for measurement of cytokines, biomarkers and blood eosinophil count. For those patients in PK group, an additional 35 ml of blood will be collected over an additional 7 times points (pre-dose, 0.5 hour, 1 hour, 2 hour, 3 hour, 4 hour, and 8 hour). Unused study medication will be collected and pill count will be recorded. Study drug will be administered in the clinic after the pre-dose PK blood draw.

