6.2.4 Followup Visits

Visit 3 Day 15-22 RANDOMIZATION VISIT

Procedures Performed:

- Administer questionnaires (ACT, QOL, A2WR)
- Review medical history, conmeds, and AEs since the screening visit
- Confirm medication washouts (reschedule if not met)
- Vitals
- Urine Pregnancy Test (if applicable)
- Physical Exam
- Review Randomization Inclusion/Exclusion Criteria
- Baseline GI side effect check list
- Randomize
- Measure Exhale Nitric Oxide (FeNO)

- Pre-dose Spirometry
- Blood draw cytokines, biomarkers and blood eosinophil count
- Pre-dose Pharmacokinetic blood draw for select subjects
- Administer 1st dose of study drug
- Post-Dose Spirometry (1 hr post-study drug dosing)
- Pharmacokinetic blood draw for select subjects (n =8 4 Males & 4 Females) (Time 0.5, 1, 2, 3, 4 & 8 hrs)- **PK Subgroup only.**
- Dispense drug

Visit 3A Day 29-36: Phone contact to answer questions and encourage compliance.

Visit 4 Day 43-50 (Day 28 of study drug):

Procedures Performed:

- Administer questionnaires (ACT, QOL, A2WR)
- Review conmeds, and AEs since V3
- Review study drug compliance (pill count)
- Confirm medication washouts (reschedule if not met)
- GI side effect checklist
- Vitals
- Urine Pregnancy Test (if applicable)
- Physical Exam
- Exhale Nitric Oxide (FeNO)
- Spirometry
- Perform Methacholine Challenge --- reschedule visit if FEV1 is < 60% or 1.5L
- Administer bronchodilator
- Methacholine Recovery Challenge
- Blood draw cytokines, biomarkers and blood eosinophil count
- Pre-dose Pharmacokinetic blood draw--**PK subgroup only.**
- Study Drug Dosing
- Pharmacokinetic blood draw (Time 0.5, 1, 2, 3, 4 & 8 hrs)—**PK subgroup only.**

Visit 4A Day 44-70: Phone or email contact to answer questions and encourage compliance.

Visit 5 Day 71-78 (Day 56 of study drug)

Procedures Performed:

- Administer questionnaires (ACT, QOL, A2WR)
- Review conmeds, and AEs since the previous visit (V4)
- Review study drug compliance (pill count)
- Confirm medication washouts (reschedule if not met).
- GI side effect check list
- Vitals
- Urine Pregnancy Test (if applicable)
- Physical Exam
- Exhale Nitric Oxide (FeNO)
- Spirometry
- Perform Methacholine Challenge --- reschedule visit if FEV1 is < 60% or 1.5 L
- Administer bronchodilator
- Methacholine Recovery Challenge
- Collect Blood for cytokines, biomarkers and eosinophil count
- Pre-dose Pharmacokinetic blood draw--**PK subgroup only.**
- Study Drug Dosing for PK group only

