7.1 Specification of Safety Parameters

- ***Methacholine challenge*** involves the inhalation of an agonist to induce bronchoconstriction and may induce the symptoms of an asthma exacerbation (chest tightness, dyspnea, coughing). The procedure is performed in a closely monitored clinical environment, with availability of bronchodilator. This procedure has been safely used in many previous studies by our group; we will only perform this procedure if the baseline FEV₁ is > 60% predicted.
- ***Bronchodilator*** (albuterol/salbuterol) will be available to be administered if the participant is uncomfortable from the effects of the methacholine challenge test.
- ***GI side effects*** will be assessed at each study visit.
- ***Venous Blood Draw***: Rarely, people faint after blood drawing and therefore will be seated during blood draws. Very rarely, the vein in which the needle has been inserted may become inflamed or infected.

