8. INTERVENTION DISCONTINUATION

Adverse gastrointestinal events associated with the consumption of ginger that require medical intervention (intravenous fluid administration, hospital admission) will prompt temporary suspension of enrollment and/or study interventions until a complete safety review is convened. Adverse reactions to inhaled methacholine that require hospital admission will prompt temporary suspension of enrollment and/or study interventions until a complete safety review is convened. Subsequent review of serious, unexpected, and related AEs by the DSMB, Independent Safety Monitor(s), IRB or the FDA may also result in suspension of further study interventions/administration of study product. The FDA retain the authority to suspend additional enrollment and study interventions/administration of study product for the entire study, as applicable.

Participants will continue to be followed with their permission if study intervention is discontinued. Temporary discontinuation of treatment would interrupt the consecutive 56 day treatment plan and thus subjects would be removed from the study. If a subject is removed from the study, evaluations related to any adverse events would be continued as defined in section 7.5 above.

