9.2 Sample Size and Randomization

We utilized published literature to identify the magnitude of change in our primary outcomes that are clinically relevant. As illustrated in the table in section 3, we calculated a need of 14 subjects per arm for the methacholine measurement and 16 subjects per arm for the exhaled nitric oxide assessment (same subjects studied in methacholine and exhaled nitric oxide assays). Thus we need 16 subjects per arm and anticipate a 10% attrition rate overall requiring 36 subjects. As illustrated in the table in section 3, an enhanced tolerance to inhaled methacholine of 0.7X the doubling dose is considered clinically significant.¹² We anticipate a S.D. of 0.6 in both groups and aim to achieve 80% power at the 0.05 significance level. This requires 14 subjects for each of the two arms. For exhaled nitric oxide with baselines starting at >50ppb, a 20% decrease is considered clinically significant. We expect a S.D. of ~ 37 and aim to achieve 80% power at the 0.05 level and will thus require 16 subjects for each of two arms.

Treatment Assignment Procedures

Subjects will be randomized to treatment A or B in a blinded fashion using the randomization algorithm within REDCap. The randomization module in REDCap implements a defined randomization model within the project, allowing the site to randomize the subjects. In this module, randomization model is defined as Drug A and Drug B in a 1:1 ratio. Drug A and Drug B may refer to placebo or active drug, however they are left coded as such to ensure blinding. The module creates a template allocation table, which the user uses to structure the randomization table to be imported. The module also monitors the overall allocation progress and assignment of randomized subjects to ensure balanced proportions of active drug and placebo. Only one site member will be allowed randomization privileges, but the site will confirm, and lock the specific data field to ensure that no data is altered after randomization. There is no stratification, and there are no variable block sizes.

Trial randomization codes for each individual subject will be retained within the REDCap data set as treatment A or B. The independent statistician retains the identity of A or B and does not disclose this to the study conductors. The planned breaking of the code will occur after data analysis is complete. Unplanned breaking of the code will occur if a medical condition mandates such an action.

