9.6 Data Analyses

We will compare the change in log-transformed methacholine reactivity (PD₂₀) in the ginger versus the placebo group using two-sample t-test. We will compare patients' initial PD₂₀ (day 0) to their subsequent PD₂₀ at days 28, 56 using paired t-test. It is possible that the PD₂₀ measurements on days 0, 28 and 56 could be influenced by the consumption of oral ginger 1 hour prior so we will also compare the PD₂₀ at

day 0 to those at 28 and 56. An acute benefit in methacholine tolerance will be reflected in a significant improvement between PD₂₀'s at days 0, 28 and 56 while a chronic improvement will be reflected in improved PD₂₀'s at days 28 and 56 compared to day 0.

Patients with asthma have remarkably consistent fractional exhaled nitric oxide (FeNO) levels when measured over time with mild-moderate asthmatics having FeNO values of approximately 40 ± 10 ppb.²² We will consider a 25% change in FeNO as biologically significant²³ comparing each patient's initial FeNO to their subsequent FeNO at days 28, 56 using paired t-test.

Data from prior studies does not support the existence of significant differences in the intervention effect between subgroups and thus subgroup analysis will not be performed.

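### Section 9.3 promises that every randomised subject is in the primary analysis, but the between-arm PD20 test in 9.6 can use only subjects with a follow-up value, and no missing-data method is given

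*Combined protocol and SAP*

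**What the plan says.** **Population.** Section 9.3: "All randomized subjects will be included in the primary analysis, analyzed based on intention-to-treat". A per-protocol analysis is secondary and excludes subjects who missed 30% or more of treatment.

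**Method.** Section 9.6 compares the change in log PD20 "in the ginger versus the placebo group using two-sample t-test". It gives no time point for that comparison. Days 28 and 56 are named for the within-patient paired t-tests. FeNO has only a paired t-test, with no between-arm test. No imputation, likelihood-based model, worst-value rule or missing-data sensitivity analysis appears.

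**Where outcomes can be lost.**
- Section 9.2: "Thus we need 16 subjects per arm and anticipate a 10% attrition rate overall requiring 36 subjects".
- Section 3, Visit 4: "Methacholine test will be performed if subject meets safety criteria". Visit 5 has the same condition: "Methacholine hyperresponsiveness will be measured if subject meets safety criteria".
- Section 6.2.4: "Perform Methacholine Challenge --- reschedule visit if FEV1 is < 60% or 1.5L". Section 6.2.5 repeats this for Visit 5.
- Section 7.1: "we will only perform this procedure if the baseline FEV₁ is > 60% predicted".
- Section 8: "Temporary discontinuation of treatment would interrupt the consecutive 56 day treatment plan and thus subjects would be removed from the study". The sentence before it says that participants whose intervention is discontinued are still followed, with their permission.
- Section 10.3.4 removes subjects for significant deviations. Its examples are not taking the capsules and missing the visit windows.

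**The concern.** A t-test on change needs a baseline and a follow-up value for each subject. Anyone without the second value drops out of the calculation, so the set analysed is randomised subjects with a follow-up PD20, which is not what 9.3 claims. Removing subjects for non-compliance or treatment interruption works against the intention-to-treat label in the same way.

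Who is lost matters more than how many. A subject whose FEV1 stays below the challenge criterion has plausibly done badly, and that subject has no PD20. If one arm has more such subjects, a completer comparison flatters that arm. Removal after interruption may also be related to tolerability. At 18 per arm, a few subjects can move the estimate noticeably.

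The test also leaves unused the baseline value as a covariate and, for a subject seen only at Visit 4, the Day 28 measurement.

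**Working it through.** **1. Reproduce the plan's sample size.** Inputs from sections 3 and 9.2: SD 0.6, alpha 0.05 (two-sided assumed, because sidedness is not stated), power 80%, 10% attrition.
- PD20: the table means differ by 1.73 − 1.07 = 0.66. The standardised difference is 0.66/0.6 = 1.10, and the two-sample t-test needs 14.0 per arm. The plan says 14. With 0.7 it needs 12.6, so 13.
- FeNO: 74 − 37 = 37 ppb with SD 37 gives 16 per arm by the normal approximation (16.7 by the t-test). The plan says 16.
- Attrition: 32/0.90 = 35.6, so 36.

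The plan's figures reproduce. They rest on 32 evaluable subjects of 36 randomised, so the calculation itself allows for about 4 subjects without an outcome. That number is an upper figure for subjects with no change score at all, because anyone who leaves after Visit 4 still has a Day 28 change.

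**2. Does the loss threaten power?** PD20 t-test, SD 0.6:

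| Evaluable per arm | Power for 0.66 | Power for 0.7 |
|---|---|---|
| 18 | 89% | 93% |
| 16 | 85% | 89% |
| 14 | 80% | 84% |
| 12 | 73% | 78% |

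Four missing values per arm (22%) can be absorbed.

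**3. How far could informative loss move the estimate?** Illustrative assumptions, not in the documents: no true effect, normal change with SD 0.6 in both arms, and the worst responders missing from one arm only. The remaining mean in that arm rises by 0.6 × S/(18 − k), where k is the number lost and S is the expected sum of the k most extreme of 18 standard normal values.
- k = 2: S = 3.17, shift = 0.6 × 3.17/16 = 0.12 doubling doses.
- k = 4: S = 5.08, shift = 0.6 × 5.08/14 = 0.22 doubling doses.

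Against the 0.7 target these are 17% and 31%. A large-sample truncated-normal formula gives 0.13 and 0.23.

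**4. What would baseline adjustment add?** With equal variances σ² at baseline and follow-up and correlation r, the change score has variance 2σ²(1 − r) and the baseline-adjusted residual has variance σ²(1 − r²). The ratio is (1 + r)/2. With the change SD held at 0.6, the adjusted SD is 0.6 × √((1 + r)/2). Power for 0.66 at 16 per arm, where the unadjusted figure is 85%:

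| r | Variance ratio | Adjusted SD | Power | Implied between-patient SD, 0.6/√(2(1 − r)) |
|---|---|---|---|---|
| 0.3 | 0.65 | 0.484 | 96% | 0.51 |
| 0.5 | 0.75 | 0.520 | 94% | 0.60 |
| 0.7 | 0.85 | 0.553 | 90% | 0.77 |
| 0.9 | 0.95 | 0.585 | 87% | 1.34 |

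The documents give no r. They also do not label 0.6 as the SD of a change. The last column shows that the larger gains require patients to be quite alike at baseline. The degree of freedom spent on the covariate is ignored.

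**The case against.** The strongest reply is that this is a 36-subject pilot, attrition is already budgeted, and power survives it. That stands: the sample size is not at fault. Inflating N, however, corrects neither a mis-stated analysis set nor a biased comparison.

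Several stronger readings are tempting, and the documents do not support them.
- *A reader might infer that anyone with a low FEV1 at Visit 4 or 5 loses the PD20.* Sections 6.2.4 and 6.2.5 reschedule the visit first. A value is lost only if FEV1 stays low, and the text does not say what happens then. No frequency can be drawn from the documents.
- *A reader might infer that 9.6 tests Day 28 and Day 56 separately between arms.* It gives the two-sample test no time point. The gap is an unspecified time point.
- *A reader might extend the FEV1 argument to FeNO.* FeNO is not conditional on FEV1. It is exposed only to attrition and removal, and its own gap is the lack of any between-arm test.
- *A reader might expect a mixed model to deliver the promised analysis of all randomised subjects.* It still omits anyone with no follow-up value, and it assumes data are missing at random. That is why 9.3 must also be reworded and a sensitivity analysis added.

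It is also fair to say that baseline adjustment is a gain in efficiency and does not repair the missing data. At r = 0.9 it adds only about 2 percentage points of power.

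**Conclusion.** The point holds in this form: 9.3 and 9.6 disagree about who is analysed, the protocol's own rules make missing PD20 values foreseeable, and nothing says how they are handled. The number with no usable change is up to about 4 of 36 under the plan's attrition figure. The possible bias of about 0.12 to 0.22 doubling doses is a one-sided worst case under a normal model with change SD 0.6. It is not a forecast. That the group with persistently low FEV1 is informative for PD20 is plausible, but the documents do not establish it.

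The gain from the recommended model, 85% to between 87% and 96% power, rests on two assumptions: that 0.6 is the SD of change, and that r lies between 0.3 and 0.9.

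This should be corrected before unblinding. It does not invalidate the design.

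**What to change.** 1. **Section 9.6, primary analysis.** Replace the two-sample t-test with a repeated-measures model for log2 PD20 over Days 28 and 56, with arm by visit, baseline by visit and unstructured covariance. Make the Day 56 arm contrast primary. Log2 puts the estimate in doubling doses. Specify the same model for log FeNO, which gives that outcome a between-arm comparison. The paired t-tests can remain as description.
2. **Section 9.6, sensitivity analysis for PD20.** Add a rank-based between-arm test that gives the worst rank to subjects not challenged because FEV1 stayed too low after rescheduling. Record the reason for every missing PD20 so that this group can be identified.
3. **Section 9.3.** Define the primary set as randomised subjects with at least one follow-up value, analysed as randomised, and report by arm the number excluded.
4. **Reconcile the passages that decide who has an outcome.** These are the removal rules in sections 8 and 10.3.4 against 9.3, the two statements in section 8 on follow-up after discontinuation, and the differing FEV1 wordings in sections 3, 6.2.4, 6.2.5, 7 and 7.1. Which clinical criterion applies is for the investigators to settle.

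The cost is revised wording and slightly more programming, with no new measurements. The downside is that the primary model assumes data are missing at random; step 2 probes that assumption for PD20.

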9.4 Interim Analyses and Stopping Rules

No interim analysis is planned. Due to the extensive use of this same formulation of ginger extract in the same daily dose, we expect no safety concerns and excellent tolerance. We have greatly exceeded these enrollment numbers in numerous previous asthma clinical studies in the John Edsall-John Wood Asthma Center at Columbia University Medical Center and believe that it is highly unlikely that this study will demonstrate poor study performance.

Adverse gastrointestinal events associated with the consumption of ginger that require medical intervention (intravenous fluid administration, hospital admission) will prompt temporary suspension of enrollment and/or study interventions until a complete safety review is convened. Adverse reactions to inhaled methacholine that require hospital admission will prompt temporary suspension of enrollment and/or study interventions until a complete safety review is convened. Subsequent review of serious, unexpected, and related AEs by the DSMB, Independent Safety Monitor(s), IRB or the FDA may also result in suspension of further study interventions/administration of study product. The FDA retain the authority to suspend additional enrollment and study interventions/administration of study product for the entire study, as applicable.

9.5 Outcomes

Outcomes will be analyzed when all patients have completed the study at day 56 by both PIs and the statistical consultant on this study ([name]) who will be blinded from the study group until the data analysis is completed.

9.5.1 Primary Outcome

The primary outcomes are a clinically significant change in tolerance to inhaled methacholine (PD₂₀) or a clinically significant change in exhaled nitric oxide. These outcomes will be measured at visit 3 (baseline) and visits 4 and 5 (days 28 and 56 of the oral ginger or placebo consumption).

9.5.2 Secondary Outcomes

Secondary outcome measures: A clinically significant increase in baseline FEV₁ of 100ml. For subjects with eosinophilia (>300 cells/ul) a 32% decrease in blood eosinophils¹⁵, a 40% decrease in serum IL4^{16,17}, a 50% decrease in serum IL5¹⁸ or a 75% decrease in serum IL13¹⁹

9.6 Data Analyses

We will compare the change in log-transformed methacholine reactivity (PD₂₀) in the ginger versus the placebo group using two-sample t-test. We will compare patients' initial PD₂₀ (day 0) to their subsequent PD₂₀ at days 28, 56 using paired t-test. It is possible that the PD₂₀ measurements on days 0, 28 and 56 could be influenced by the consumption of oral ginger 1 hour prior so we will also compare the PD₂₀ at

day 0 to those at 28 and 56. An acute benefit in methacholine tolerance will be reflected in a significant improvement between PD₂₀'s at days 0, 28 and 56 while a chronic improvement will be reflected in improved PD₂₀'s at days 28 and 56 compared to day 0.

Patients with asthma have remarkably consistent fractional exhaled nitric oxide (FeNO) levels when measured over time with mild-moderate asthmatics having FeNO values of approximately 40 ± 10 ppb.²² We will consider a 25% change in FeNO as biologically significant²³ comparing each patient's initial FeNO to their subsequent FeNO at days 28, 56 using paired t-test.

Data from prior studies does not support the existence of significant differences in the intervention effect between subgroups and thus subgroup analysis will not be performed.

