3. STUDY DESIGN

A placebo controlled, double blind, randomized clinical pilot study of mild to severe asthmatics treated in a 1:1 ratio with oral ginger 1 gm twice per day or matching placebo.

18 subjects will be assigned to each of two arms (ginger vs. placebo). This is defined by a power analysis requiring 16 subjects per arm and a 10% projected attrition rate. Subjects will be evaluated 5 times during the study, at screening, baseline methacholine testing, at the initial randomization visit and at days 28 and 56 while taking ginger or placebo.

The primary outcomes will be the improved tolerance to the bronchoconstrictive effect (reduced airway hyperresponsiveness) of inhaled methacholine (methacholine PD₂₀) or a reduction in exhaled nitric oxide. Secondary outcomes will include an improvement in baseline FEV1 of 100ml, a reduction in eosinophilia or a reduction in asthma associated serum cytokines. An additional secondary outcome will be defining the pharmacokinetic profile of active components of ginger in adult asthmatics.

Grant phase	Spec. Aim	Primary outcome	Clinically Significant Change [ref]	Means ± S.D; examples from literature [ref] (units)	Sample Size \group	# of groups	Sample size required	Sample Size required with 10% attrition
R61	1	Mch PD ₂₀ doubling dose	Increase of 0.7 in Mch doubling dose ¹²	1.07 ± 0.6 1.73 ± 0.6 (Mch doubling dose) ¹²	14	2 2g/day ginger placebo	28	32
	2	Exhaled nitric oxide	20% decr for >50 ppb or decr of 10ppb for <50ppb ¹³	74 ± 37 37 ± 34 (ppb) ¹⁴	16	2 2g/day ginger placebo	32	36 for aims 1&2

Outpatient; The John Edsall-John Wood Asthma Center at the Columbia University Medical Center

Individual enrollment: 78 +/- 7 days. Enrollment period 12 months, Entire trial (first subject screened to last patient completed): 20 months.

Screening/Run-In Period

Adults 18 and older, with physician diagnosed mild to severe persistent asthma will be screened. After reviewing and signing informed consent, subjects that fulfill inclusion and exclusion criteria will be invited to participate.

Day 0/Visit 1: Screening Visit: review of medical history, recording of medication use, physical exam by study MD or NP, scoring on ACT and basic spirometry before and after bronchodilator. Subjects will then be asked to continue their usual asthma medications for the 14-21 day run-in period.

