6.2.1 Screening Evaluation

Adults 18 and older, with physician diagnosed mild to severe persistent asthma will be screened. After reviewing and signing informed consent, subjects that fulfill inclusion and exclusion criteria will be invited to participate.

Consenting Procedure

Single informed consent describing screening and study procedures.

The study PI ([name]) or the research study coordinator ([name]) will conduct the consent process.

[name] is a professor of medicine and pulmonologist and director of the John Edsall-John Wood Asthma Center at Columbia University Medical Center. [name], B.S. has over 3 years of experience as a clinical research coordinator and has experience consenting and studying pulmonary

patients during clinical studies in the John Edsall-John Wood Asthma Center.

Any changes in the consent form will only occur after approval from the institutional IRB and the NCCIH.

Documentation of the consent process and consent forms will be retained in a research study binder.

Screening

Visit 1: Screening Visit

Sequence of events:

- Identify patients that are adults 18 and older with physician-diagnosed mild to severe persistent asthma
- Sign informed consent
- Fulfill inclusion and exclusion criteria
- Review of medical history
- Record Demographics
- Recording of medication use
- Physical exam including vital signs by study MD or NP
- Urine pregnancy test for women of child bearing age
- Scoring on ACT ≤ 19
- Scoring on basic spirometry before and after bronchodilator

Required to be eligible:

- Patients that are adults 18 and older with physician-diagnosed mild to severe persistent asthma
- Signing informed consent
- Fulfill inclusion and exclusion criteria
- Using inhaled corticosteroids with or without inhaled long acting beta agonists or anti-muscarinics.
- Scoring on ACT ≤ 19
- Negative urine pregnancy test for women of child bearing age

Screening must be completed 14-21 days prior to visit 2 during which the ACT score will be confirmed to be ≤ 19 , and the baseline FEV1 is $\geq 60\%$ of predicted (or 1.5L); Baseline methacholine PD20 will be determined at V2 as a subsequent eligibility criterion.

Visit 2; Day 14 to 21:

- Administer ACT. If ACT remains ≤ 19 , proceed . If ACT > 19 consistent with good asthma control, terminate from study.
- Confirm medication washouts (reschedule if not met).
- Spirometry

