6.2.2 Enrollment, Baseline, and/or Randomization

Enrollment

A single informed consent form will be used for screening and enrollment. The enrollment date will be defined as the date that all of the screening criteria are met and the individual agrees to participate.

The enrollment date will be recorded on the case report form and the allowable window from enrollment to randomization will be 15-22 days.

Baseline Assessments

- Baseline FEV1
- Baseline methacholine PD20
- Baseline ACT score

- Baseline QOL and Asthma 2 week recall questionnaires
- Baseline GI symptoms
- Baseline Exhaled Nitric Oxide
- Blood draw for eosinophils, cytokines, biomarkers
- Blood draw for metabolite measurements in subjects participating in PK study

Randomization

Randomization to initiation of study intervention will occur on the same day. Randomization will occur at visit 3 and will precede an intervention (i.e. starting of oral ginger or placebo).

Randomization is a process that assigns participants/subjects by chance (rather than by choice) into specific groups, typically for clinical research and clinical trials. An independent statistician will generate the randomization codes and allocations. The blinded study coordinator will retrieve the randomization allocation through RedCap. RedCap is an institutionally available automated system for randomization and the independent statistician will have direct oversight over the process. The blinded study team will not have access to the randomization codes. In this module, randomization model is defined as Drug A and Drug B in a 1:1 ratio. Drug A and Drug B may refer to placebo or active drug, however they are left coded as such to ensure blinding. The module creates a template allocation table, which the user uses to structure the randomization table to be imported. The module also monitors the overall allocation progress and assignment of randomized subjects to ensure balanced proportions of active drug and placebo. Only one site member will be allowed randomization privileges, but the site will confirm, and lock the specific data field to ensure that no data is altered after randomization. There is no stratification, and there are no variable block sizes..

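### The between-arm test of PD20 is valid but does not adjust for baseline PD20; a pre-specified baseline-adjusted model would probably add a few points of power and needs no new data

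*Combined protocol and SAP*

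**What the plan says.** Section 9.6 compares the change in log PD20 "in the ginger versus the placebo group using two-sample t-test". The other tests in that section are within-patient. FeNO, the second primary outcome, is handled by "comparing each patient's initial FeNO to their subsequent FeNO at days 28, 56 using paired t-test", and no between-arm FeNO test is named. No covariate-adjusted model appears anywhere in the document.

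Section 6.2.1 says that "Baseline methacholine PD20 will be determined at V2 as a subsequent eligibility criterion", and section 6.2.2 lists "Baseline methacholine PD20" among the baseline assessments. The schedule in section 6.1 has methacholine testing at Visits 2, 4 and 5. Sections 9.1 and 9.5.1 place the baseline elsewhere. Of both primary outcomes, 9.5.1 says: "These outcomes will be measured at visit 3 (baseline) and visits 4 and 5". The schedule has no methacholine test at Visit 3.

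For sample size, the table in section 3 gives "Increase of 0.7 in Mch doubling dose" as the clinically significant change, with literature values of 1.07 and 1.73 doubling doses, each with SD 0.6. Section 9.2 adds: "We anticipate a S.D. of 0.6 in both groups and aim to achieve 80% power at the 0.05 significance level". The result is 14 per arm for PD20. FeNO raises this to 16 per arm, and 10% attrition raises it to 36 randomised, 18 per arm. Randomisation is not stratified.

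**The concern.** A change score uses the baseline only by subtraction, which fixes the slope of follow-up on baseline at 1. If baseline and follow-up correlate at less than 1, subtraction over-corrects. A participant with a high baseline tends to show a smaller rise (or a fall) through regression to the mean, and that variation stays in the error term.

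Two things are at stake. One is precision on the only primary outcome with a written randomised comparison. The other is that, with about 16 to 18 per arm and no stratification, the arms can differ by chance in baseline PD20, and the change-score estimate moves with that difference. The plan gives no reason for leaving baseline out of the model.

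**Working it through.** **Inputs from the plan.** Difference 0.66 (1.73 − 1.07, section 3) or 0.70 (sections 3 and 9.2); SD 0.6 in each arm; alpha 0.05; 14 per arm for PD20 and 16 evaluable per arm overall.

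**Assumptions.** The test is two-sided (not stated). The 0.6 is the SD of change. The variance is the same at baseline and follow-up. Rho is not given in the documents, so a range is shown.

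**The plan's own figure.** Noncentral-t power for a two-sample t-test with SD 0.6 and difference 0.66 is 79.99% at 14 per arm, so the stated 14 per arm for 80% power reproduces. At 16 per arm, power is 85.3% (difference 0.66) or 89.1% (difference 0.70). Attrition: 32/0.9 = 35.6, rounded up to 36, as stated.

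**Variance with and without the covariate.** Let s be the SD of log2 PD20 at one visit.

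- Change score: 2(1 − rho)s².
- Baseline-adjusted: (1 − rho²)s².
- Ratio, adjusted to change: (1 + rho)/2. At rho 0.5 this is 0.75, so the SD falls from 0.600 to 0.6 × √0.75 = 0.520.

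Estimating the slope has a price: one degree of freedom (2n − 3 instead of 2n − 2) and a variance inflation of 1 + 1/(2n − 4), which is 1.042 at n = 14 and 1.036 at n = 16. Both are included below.

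**Change in power (percentage points), adjusted model minus t-test on change.**

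| Difference, n per arm | t-test power | rho 0.3 | 0.5 | 0.7 | 0.8 | 0.9 | 0.95 |
|---|---|---|---|---|---|---|---|
| 0.66, 14 | 80.0% | +12.5 | +8.6 | +4.4 | +2.4 | +0.3 | −0.7 |
| 0.66, 16 | 85.3% | +10.3 | +7.3 | +4.0 | +2.3 | +0.5 | −0.4 |
| 0.70, 14 | 84.4% | +10.6 | +7.5 | +3.9 | +2.1 | +0.3 | −0.7 |
| 0.70, 16 | 89.1% | +8.2 | +6.0 | +3.4 | +1.9 | +0.4 | −0.4 |

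With all 18 per arm evaluable, the gain at rho 0.5 is 6.0 points (0.66) or 4.6 points (0.70). Simulation of 40,000 trials per cell, run for rho 0.5 to 0.9, agreed with the calculated gains to within about 0.3 points.

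**What rho implies about entry PD20.** With the SD of change fixed at 0.6, s = 0.6/√(2(1 − rho)): 0.60 doubling doses at rho 0.5, 0.77 at 0.7, 1.34 at 0.9. A wide spread of entry PD20 therefore goes with a high rho and a small gain.

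**If 0.6 is instead the SD at a single visit**, the rho 0.5 figures are unchanged. At 14 to 16 per arm the gain is about 14 to 16 points at rho 0.3. At rho 0.7 it is at most 2 points, because the t-test on change already has at least 95% power.

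**Chance imbalance.** If the arms differ at baseline by D, the change-score estimate is expected to shift by (1 − rho)D in the opposite direction. For a one-standard-error imbalance at 16 per arm, D = s√(2/16):

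- rho 0.5: 0.5 × 0.60 × 0.354 = 0.11 doubling doses, 16% of 0.66
- rho 0.7: 0.3 × 0.77 × 0.354 = 0.08, 12%
- rho 0.9: 0.1 × 1.34 × 0.354 = 0.05, 7%

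The adjusted model removes this component.

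**The case against.** The strongest reply is that nothing is broken. A t-test on change is valid under randomisation, is unbiased over repeated randomisation, already uses each participant's baseline, and matches the sample-size calculation if 0.6 is the SD of change. At 16 evaluable per arm it has 85% to 89% power against a target of 80%, in a study described as a pilot. All of that stands, and it is why this is an efficiency refinement.

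The second reply is that the gain may be small. The trial enrols mild to severe asthma, and the PD20 entry criterion has only an upper limit, so entry values could be widely spread. As an illustration and an assumption only, values spread evenly over five doublings have an SD of 5/√12 = 1.44. With the SD of change at 0.6, that implies rho = 1 − 0.36/(2 × 1.44²) = 0.91, where the gain is under half a point at 16 per arm. This also stands: the documents do not show where in the range rho lies.

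A reader might infer a firm gain of 7 to 10 points at no cost. The documents do not support that. It needs rho near 0.5 or lower, which they do not give. Even at rho 0.5, the gain at a difference of 0.70 with 16 per arm is 6.0 points, and slope estimation has a small price that exceeds the benefit at rho 0.95. What the replies do not remove is the asymmetry: several points may be gained, less than one may be lost, and the sensitivity to chance imbalance goes.

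**Conclusion.** The point holds as a recommended improvement. The planned comparison is valid and meets its power target, but it leaves out a baseline measurement that every correctly enrolled participant has, without a stated reason.

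The size rests on four assumptions: the unknown rho, 0.6 as the SD of change, equal variance at both visits, and two-sided testing. Confidence in the direction is good for rho up to about 0.9. Confidence in any single figure is low.

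A reader might also infer that the PD20 analysis is biased or the trial underpowered. Neither follows. The shift from baseline imbalance belongs to a particular sample and averages to zero over randomisations.

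The missing between-arm test for FeNO, in the same section, is the weightier gap. It is a separate point, and this change does not repair it.

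**What to change.** In section 9.6, make the between-arm PD20 analysis a linear model of follow-up log2 PD20 on treatment arm and Visit 2 log2 PD20. Report the adjusted ginger-minus-placebo difference in doubling doses with its 95% CI, and keep the two-sample t-test on change as a sensitivity analysis. State whether day 28 or day 56 is the follow-up for the primary comparison, since 9.6 does not choose.

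In sections 9.1 and 9.5.1, name Visit 2 as the PD20 baseline, so that they agree with sections 6.1 and 6.2.1.

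The cost is a few sentences, one degree of freedom and the slope-estimation penalty: under one point of power at worst over the range of rho examined. No new data, visits or patients are needed. Fixing the model in advance also closes the choice between adjusted and unadjusted results after the data are seen.
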